5.6.3. Hormonal Contraceptives

Pexidartinib has been indicated to be a moderate CYP3A4 inducer, as concurrent administration of pexidartinib decreased the area under the plasma-concentration-time curve from time zero to infinity (AUCinf) of the CYP3A4 substrate midazolam by 57%. As the hormonal contraceptive ethinyl estradiol is a CYP3A4 substrate, there is a potential that exposure of ethinyl estradiol may decrease on concurrent administration with pexidartinib. As pexidartinib may cause embryo-fetal harm when administered to a pregnant woman, females of reproductive potential should be advised to use an effective, non-hormonal method of contraception during treatment with pexidartinib and for 1 month after the last dose. Males with female partners of reproductive potential should be advised to use an effective method of contraception during treatment with pexidartinib and for 1 month after the last dose. Female partners of male patients should concurrently use effective contraceptive methods (hormonal or non-hormonal).

5.6.4. Acid-reducing Agents

Avoid the concomitant use of PPIs while taking pexidartinib. As an alternative to a PPI, administer pexidartinib 2 hours before or 2 hours after taking a locally-acting antacid, or if using a histamine 2 (H_2)-receptor antagonist, administer pexidartinib at least 2 hours before or 10 hours after taking an H_2 -receptor antagonist.

5.7. Dosage Modification for Renal Impairment

The recommended dosage of pexidartinib for patients with mild to severe renal impairment (CLcr 15 to 89 mL/min estimated by Cockcroft-Gault using actual body weight) is 200 mg in the morning and 400 mg in the evening.

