3. STUDY DESIGN

3.1. Overall Plan

This will be a multicenter, single arm study of pexidartinib orally administrated in adult subjects with symptomatic TGCT associated with severe morbidity or functional limitations and not amenable to improvement with surgery.

Study drug will be administered twice a day, every day. Subjects will take 400 mg twice daily for a total daily dose of 800 mg (2 capsules in the morning and 2 capsules in the evening). The study drug must be taken on an empty stomach at approximately the same time of the day with about 12-hour interval. The pexidartinib starting dose and treatment regimen in this study are based on the rationale of PLX108-10 study and the result of the Study PL3397-A-103.

The primary endpoint in this study is the proportion of subjects who achieve a CR or PR at the Week 25 based on criteria as defined by RECIST 1.1 by centrally reviewed MRI scan, the same as defined in the PLX108-10 study. The MRI will be assessed at every 3 months. A subject will be considered to have a response, if the tumor meets the criteria for response and has a documented nonprogression at Week 25. To minimize bias and reduce variability from this single-arm study, centralized review of the MRI image will be performed by blinded readers. The Imaging Charter for this study describes the image acquisition standards and methodology to be used as well as the standards for image interpretation.

It is considered that tumor shrinkage is essential to improve symptoms for advanced TGCT subjects. The improvement of symptom will be evaluated with secondary endpoints. The endpoint of TVS by the use of central MRI readers will be reinforced for the primary imaging endpoint of RECIST 1.1 assessment. The endpoint of range of motion or PROMIS will reinforce the explanation of clinical benefit from primary imaging endpoint.

The data of PLX108-01 preliminary results suggests that the use of pexidartinib offers high tumor response rate to subjects with this diagnosis who would not be adequately treated with surgery, the existing only standard of care. The use of placebo will be an expected ethical limitation to enroll subject with symptomatic and surgical resection associated with potentially worsening functional limitation or severe morbidity under the circumstances of rare disease.

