4.1. Inclusion Criteria

Subjects must satisfy all of the following criteria to be included in the study:

- 1. Age \geq 18 years (Age \geq 20 years in Taiwan).
- 2. A diagnosis of TGCT (i) that has been histologically confirmed by a pathologist and (ii) associated with severe morbidity or functional limitations and not amenable to improvement with surgery determined consensually by qualified personnel (eg, 2 surgeons or a multi-disciplinary tumor board).
- 3. Measurable disease as defined by RECIST 1.1 (except that a minimal size of 2 cm is required), assessed from MRI scan by a central radiologist.
- 4. Stable prescription of analgesic regimen during the 2 weeks prior to enrollment.
- 5. Women of childbearing potential must have a negative serum pregnancy test within the14-day period prior to enrollment (Where demanded by local regulations, this test may be required within 72 hours of enrollment).
- 6. Females of reproductive potential should be advised to use an effective, non-hormonal method of contraception during treatment with pexidartinib and for 1 month after the last dose. Males with female partners of reproductive potential should be advised to use an effective method of contraception during treatment with pexidartinib and for 1 month after the last dose. Female partners of male patients should concurrently use effective contraceptive methods (hormonal or non-hormonal). Women of nonchildbearing potential may be included if they are either surgically sterile or have been postmenopausal for \geq 1 year. Women who have documentation of at least 12 months of spontaneous amenorrhea and have a follicle-stimulating hormone level > 40 mIU/mL will be considered postmenopausal.
- 7. Adequate hematologic, hepatic, and renal function, defined by:
 - Absolute neutrophil count $\geq 1.5 \times 10^{9}/L$
 - Hemoglobin > 10 g/dL
 - Platelet count $\geq 100 \times 10^{9}/L$
 - AST and ALT $\leq 1.0 \times$ upper limit of normal (ULN)
 - Total bilirubin and direct bilirubin $\leq 1.0 \times ULN$
 - Alkaline phosphatase $\leq 1.0 \times \text{ULN}$
 - Creatinine clearance (CLcr) > 15 mL/min
- 8. Willingness and ability to complete the PROMIS Physical Function Scale.
- 9. Willingness and ability to use a diary.

10. Willingness and ability to provide written informed consent prior to any study-related procedures and to comply with all study requirements.

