5. STUDY TREATMENT

5.1. Assigning Subjects to Treatments and Blinding

5.1.1. Treatment Group

This is a single arm study. Eligible subjects will receive 400 mg twice daily for a total daily dose of 800 mg (2 capsules in the morning and 2 capsules in the evening).

Treatment duration of pexidartinib is presented in Section 3.1.1.

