5.2.4. Administration

Study drug will only be given to enrolled subjects under the supervision of the principal investigator or identified subinvestigator(s). The study drug for home administration during the study will be dispensed to the subject for the first time at the Cycle 1 Day 1 (C1D1) visit (within 3 days of enrollment). Capsules must be swallowed and not crushed, chewed, or dissolved in liquid. In this study, subjects will only receive pexidartinib capsules.

Study drug administration will begin at the C1D1 visit in the morning. At this visit, subjects will be instructed to take 400 mg BID for a total daily dose of 800 mg (2 capsules in the morning and 2 capsules in the evening) through the study. The study drug must be taken on an empty stomach at approximately the same time of the day with about 12-hour interval. Each dosing cycle will be of 28 days.

For the C1D15 visit (Week 3) and any visit when an ECG and PK will be performed, subjects must be told to NOT take their morning dose of study drug while coming for the study visit, which should be scheduled in the morning. The subject must be instructed to bring their bottle of study drug to the site and take their morning dose upon instruction by the study site. The time of dosing must be recorded. Subjects will then take their evening dose at home. If dose administered at the site is taken in the afternoon, then the subject must be instructed to skip their evening dose for that day.

For the C7D1 visit (Week 25), subjects must be told to NOT take the morning dose of study drug before their visit and bring all unused capsules to the site for accountability. Subjects who continue the study will be taking the same number of pexidartinib capsules per day as they will be taking at the end of 24 weeks treatment, ie, a maximum dose of 800 mg/day pexidartinib.

Between site visits, subjects are to administer their study drug at home and record the dosing information in the study dosing diary. Missed doses (those generally outside of $a \pm 2$ hours dosing window) must be skipped and NOT administered as a double dose at the next dosing time point. Subjects who vomit their dose must be instructed NOT to make up that dose.

Further details on study drug administration are present in the Study Pharmacy Manual.

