5.4. Dose Modification

Reducing or interrupting the dose for toxicity may take place at any time during the study according to the guidelines in Table 5.1 and Table 5.2. Dose modification guidelines for hematologic and hematologic treatment-related TEAEs are based on severity. Dose interruptions can be implemented at the discretion of the treating Investigator to manage intolerable or clinically significant toxicity. If a dose interruption is required, study assessments must be performed as scheduled, irrespective of the study drug delay, with the exception of PK assessments which must be deferred until treatment is resumed.

When an odd number of capsules are taken in a day, the larger number of capsules must be taken as the evening dose. For example, 600 mg/day = 3 capsules (1 capsule in the morning and 2 capsules in the evening). When an even number of capsules per day is to be taken, the morning and evening doses must be the same (eg, 800 mg/day = 4 capsules [2 capsules in the morning and 2 capsules in the evening] or 400 mg/day = 2 capsules [1 capsule in the morning and 1 capsule in the evening]).

Dose reductions must be applied in increments of 200 mg/day (1 capsule), with a maximum total reduction of 400 mg/day (ie, a minimum dose of 400 mg/day). Subjects unable to tolerate 400 mg/day (2 capsules) will be discontinued. Once dose reduction takes place for toxicity, a dose re-escalation is generally not allowed unless approved after discussion with the DS's Medical Monitor or designee.

Dose reduction	Total daily dose	Administration of total daily dose
First	600 mg	200 mg in the morning and 400 mg in the evening
Second	400 mg	200 mg twice daily

Table 5.1:Dose Modification

Dose modification guidelines for treatment-emergent toxicities as well as guidelines for their management are presented in Table 5.2. These parameters are only a guide and are not intended to supersede the clinical judgment of the treating Investigator. All adjustments must be communicated to DS's Medical Monitor or designee. Additional liver evaluation is presented in Table 5.3. Rechallenge with a reduced dose of pexidartinib may result in a recurrence of increased serum transaminases, bilirubin, or ALP. Monitor liver tests weekly for the first month after rechallenge.

Table 5.2:	Dose Modification	Guidelines for	Treatment-emergent Toxicities
-------------------	--------------------------	-----------------------	--------------------------------------

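### The 800 mg/day regimen and the 600 mg/day renal dose in Section 5.7 are neither reconciled nor timed, and the reduction ladder in Section 5.4 is worded only for an 800 mg/day start

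*Combined protocol and SAP*

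**What the plan says.** **General regimen.** Section 3.1: "Subjects will take 400 mg twice daily for a total daily dose of 800 mg". Section 5.1.1: "Eligible subjects will receive 400 mg twice daily for a total daily dose of 800 mg". Section 5.2.4, on the C1D1 visit: "subjects will be instructed to take 400 mg BID for a total daily dose of 800 mg", continuing with "2 capsules in the evening) through the study". None of the three names a renal exception or refers to Section 5.7.

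**Renal dose.** Section 5.7 is a single sentence on the recommended dosage: "patients with mild to severe renal impairment (CLcr 15 to 89 mL/min estimated by Cockcroft-Gault using actual body weight) is 200 mg". That is the morning dose; the evening dose is 400 mg.

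**Eligibility.** Inclusion criterion 7 in Section 4.1 requires "Creatinine clearance (CLcr) > 15 mL/min".

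**Reductions for toxicity.** Section 5.4 says "Dose reductions must be applied in increments of 200 mg/day (1 capsule") and caps them "with a maximum total reduction of 400 mg/day (ie, a minimum dose of 400 mg/day"). Table 5.1 lists a first reduction to 600 mg/day, split as in Section 5.7, and a second to 400 mg/day. Several rows of Table 5.2 tell the investigator to restart at a lower dose once a laboratory value or adverse reaction has improved.

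**The concern.** For an eligible subject with CLcr above 15 and up to 89 mL/min, the protocol states two planned doses and does not say which governs. Two sites could start subjects with the same CLcr on different doses, or act differently when CLcr crosses 89 mL/min during treatment.

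The ambiguity carries into other rules. Section 5.5 measures compliance as capsules taken over capsules expected, and the expected number depends on which section is followed. Section 14.5 treats departures in dosing as reportable deviations, but for these subjects the protocol does not settle which dose would be the deviation.

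Reading Section 5.7 as the governing exception moves the difficulty into Section 5.4. The subject then already takes the regimen in the first row of Table 5.1, so a Table 5.2 instruction to restart lower, read through that row, produces no reduction. Those instructions include the ones for raised transaminases and bilirubin, so this bears on subject safety.

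**Working it through.** **1. The two doses.** Sections 3.1, 5.1.1 and 5.2.4: 2 × 400 = 800 mg/day. Section 5.7: 200 + 400 = 600 mg/day. Difference: 800 − 600 = 200 mg/day, or 200/800 = 25%. With 200 mg capsules this is 4 against 3 per day, so a subject taking 3 could be recorded as 3/3 = 100% or 3/4 = 75% compliant under Section 5.5.

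**2. The overlap.** Entry requires CLcr above 15 mL/min and Section 5.7 covers 15 to 89. Every value in the Section 5.7 range except exactly 15 is eligible on this criterion.

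**3. Section 5.4 from 800 mg/day (the plan's own figures).** Table 5.1: 800 − 600 = 200 and 600 − 400 = 200, so both rows are real steps of the required size. Maximum reduction: 800 − 400 = 400 mg/day, which equals the stated minimum. Section 5.4 is consistent from this start.

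**4. Section 5.4 from 600 mg/day.**

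| Item | From 800 | From 600 |
|---|---|---|
| Change at first row of Table 5.1 | 200 | 600 − 600 = 0 |
| Change from there to second row | 200 | 600 − 400 = 200 |
| Real steps in Table 5.1 | 2 | 1 |
| Start minus 400 mg/day | 400 | 200 |

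(All doses in mg/day.) The zero in the first row does not fit the rule of 200 mg/day increments. The sentence that equates the maximum reduction with the minimum dose needs start − 400 = 400, which is true only for a start of 800.

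**5. Timing.** Section 9.9 calculates CLcr by Cockcroft-Gault: (140 − age) × weight / (72 × serum creatinine), times 0.85 for women. Section 5.7 specifies actual body weight. In Table 16.3, up to Week 25:
- Serum chemistry, which includes creatinine, is scheduled at 8 assessments: Screening, C1D1, C2D1, C3D1, C4D1, C5D1, C6D1 and C7D1. C1D15 is hematology only. Under Section 6.3.1 the C1D1 tests are needed only if not done within the preceding 72 hours.
- Weight is scheduled at 2: Screening and C7D1.

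Creatinine could therefore prompt the question of an on-study change several times before Week 25, but the protocol does not say whether Section 5.7 then applies, or which weight enters the formula.

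**6. Comparison within the protocol.** Section 5.6.2 says when the inhibitor-related reduction starts and how the dose returns, and Table 5.4 has its own row for a planned 600 mg/day. Section 5.7 has no such timing, and Table 5.1 has no such row.

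**The case against.** **Section 5.7 may simply be a specific rule that overrides a general one.** Its heading calls it a dosage modification, it covers a defined subgroup, and it would have no effect if the general sentences always prevailed. The general sentences also carry no exception for toxicity or inhibitor reductions, which plainly apply. Section 5.2.4 itself treats 800 mg/day as a maximum for subjects who continue after Week 25. This is a fair reading, and it defeats a stronger one that a reader might infer: that the Section 5.2.4 wording is absolute, so that the sections cannot be read together. They can. But no passage states the exception, the reading supplies no timing, and it is the reading that exposes the first row of Table 5.1.

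**The limits in Section 5.4 can all be met from 600 mg/day.** One step of 200 reaches 400, which is one increment, within the maximum and at the floor. This stands. A reader might infer from 600 − 400 = 200 that Section 5.4 takes such a subject below its own minimum. It does not: a maximum reduction is not a required one, and the 400 mg/day floor is stated separately. What remains is that the equating clause and the first row of Table 5.1 are worded for one starting dose.

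**CLcr on study.** A reader might take the 8 chemistry assessments as 8 opportunities to apply Section 5.7 exactly. The weight schedule does not support that.

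**Other controls.** Section 5.4 requires all adjustments to be reported to the Medical Monitor, which limits divergence between sites. Section 5.2.4 refers further detail to a Study Pharmacy Manual that is not among the documents. The manual may settle the matter in practice, but the protocol would still need to agree with it. It is also fair that renal impairment is a status rather than an event with a start and stop date, so Section 5.7 need not mirror Section 5.6.2; it still has to say when that status is judged.

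**Conclusion.** The point holds as a failure to reconcile passages. The protocol gives planned doses of 800 and 600 mg/day, a 25% difference, for nearly the whole CLcr range of Section 5.7, without ranking them or stating when the lower one applies. If Section 5.7 is an exception, Table 5.1 offers one real reduction instead of two, and its first row is a 0 mg change.

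The consequence is limited. The 200 mg/day increment, the 400 mg/day floor and the laboratory thresholds in Table 5.2 remain in force. The primary analysis in Section 10.5.1, a proportion with a Clopper-Pearson interval, is unchanged as a method. A reader might infer a bias in the response rate; the documents do not support that, because they give neither the share of subjects with CLcr up to 89 mL/min nor a response rate by dose within this population. The number of subjects affected is therefore unknown.

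The conclusion rests on the protocol text alone and assumes that no document outside it already settles the order of precedence. It is worth correcting because it touches dosing after toxicity and needs only wording. No view is taken on which dose or rule is right.

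**What to change.** The sponsor should:

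1. Reconcile Sections 3.1, 5.1.1, 5.2.4 and 5.7 so that one planned dose applies to each eligible CLcr value, including the boundary at 15 mL/min, where the entry criterion and Section 5.7 differ.
2. State whether Section 5.7 applies at C1D1, on a later change in CLcr, or both. If it applies on study, state which weight is used in the Cockcroft-Gault formula.
3. Make Table 5.1 and the maximum-reduction/minimum-dose sentence in Section 5.4 consistent with every permitted planned dose.

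The cost is a wording amendment to whichever of these sections the reconciliation touches. Creatinine and weight are already collected at Screening, and chemistry is repeated on study. Extra weight measurements would be needed only if the sponsor chose on-study application with a current weight. The sample size and the primary analysis need no change.

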5.8. Subject Withdrawal/Discontinuation

5.8.1. Reasons for Withdrawal

The reason for discontinuation should be recorded for any subject discontinuing from the study.

The reasons a subject may discontinue or be withdrawn from the study permanently include but are not limited to:

- AE
- Disease progression
- Subject request
- Investigator decision
- Protocol violation
- Surgery
- Subject noncompliance
- Pregnancy
- Study termination by DS or institutional review board (IRB)/independent ethics committee (IEC)

During the study, if a subject experiences radiological progression documented by central read, the subject may either be withdrawn from the study or, if the subject is continuing to have clinical benefit, the Investigator may consult with DS's Medical Monitor or designee to allow the subject to remain in the study.

5.8.2. Withdrawal Procedures

If a subject is withdrawn from the study, the Investigator will complete and report the observations as thoroughly as possible up to the date of withdrawal including the date of last dose and the reason for withdrawal.

If the subject is withdrawn due to an AE, the Investigator will follow the subject until the AE has resolved or stabilized.

All subjects who are withdrawn from the study must complete protocol-specified withdrawal procedures.

When a subject discontinues or is permanently withdrawn from the study, the Investigator will notify DS and ensure that the procedures listed in the "post-treatment visit" column in the Schedule of Assessment (Table 16.3) are performed 28 ± 7 days after the subject's last dose of

study drug and prior to initiating any new TGCT therapy, including surgery, whichever occurs first.

The consequence of a subject's withdrawal of all consent will be that no new information will be collected from that subject and added to the existing data or any database. However, every effort should be made to follow all subjects for safety.

The reason for study withdrawal will be recorded. If a subject discontinues study drug to undergo surgery, information about the type of surgery and its outcome must be collected.

5.9. Long Term Follow-up

After completion of the end-of-study or early termination visit, subject status will be collected by telephone contact every 6 months as a long term follow-up at least 2 years from each subject who consent.

6. STUDY PROCEDURES

Study procedures are listed by visit in the following subsections. Additional details are provided in the MRI Procedure Manual, or Laboratory Manual as applicable.

Each subject must sign and date an ICF before undergoing any study procedure including screening procedures unless the screening procedure is considered standard of care.

Screening procedures are to be performed within 42 days before the first dose of study drug, unless otherwise noted.

If a dose interruption is required, study assessments must be performed as scheduled, irrespective of the study drug delay, with the exception of PK assessments which should be deferred until treatment is resumed.

6.1. Screening

6.1.1. Screening (Day –42 to Day –1)

The following procedures must be performed within the 42-day period before C1D1, unless otherwise noted, and the results must be obtained and evaluated for eligibility prior to the C1D1 visit:

To be performed before any procedures:

• Informed consent

Before any invasive procedures carried out on the same day, the following parameters are to be recorded:

- Vital signs, including blood pressure (BP), pulse rate, and temperature
- 12-lead ECG

Other procedures to be performed:

- Medical history (including TGCT treatment history and smoking history)
- Demographics, including ethnicity and race
- Assessment of concomitant medications including analgesics
- PROMIS Physical Function Scale
- EQ-5D-5L
- Surgical Assessment Questionnaire
- Height and weight
- Physical examination
- Clinical laboratory tests: serum chemistry, hematology, liver function, hepatitis panel, hormone testing (as applicable)*, serum pregnancy testing (as applicable)**
- MRI of the affected joint within 56 days prior to C1D1
- Photographic documentation of tumor

- Range of motion assessment of the affected joint
- AE assessment
- Serum sample for anti-mitochondrial antibody (AMA)

* Note: Women who are not using hormonal contraception must be tested for levels of follicle-stimulating hormone (FSH), luteinizing hormone (LH), progesterone, and estradiol. Hormone testing will not be required for women who have either had an oophorectomy or are postmenopausal. Men must be tested for levels of LH, FSH, and testosterone. Men whose testosterone level is below baseline at the last study visit must be followed until their level has stabilized or returned to baseline.

** Note: Women of childbearing potential must have a serum pregnancy test within 14 days of enrollment (or, where different regulations apply, within 72 hours of enrollment). Women who have documentation of at least 12 months of spontaneous amenorrhea and have an FSH level > 40 mIU/mL will be considered postmenopausal and need not undergo pregnancy testing.

